Conditioned Pain Modulation consists of the reduction of the pain provoked by a given noxious stimulus (i.e., test stimulus) when another painful stimulus (i.e., conditioning stimulus) is applied to a remote area (i.e., pain inhibits pain; Yarnitsky et al., 2010; Willer et al., 1984); whereas TSSP occurs when repeated noxious stimuli over the same corporal area amplifies pain sensations, probably due to a central sensitization derived from the enhanced response of dorsal horn neurons to repetitive nociceptive signals from C-fibers (Dickenson, 1997). Concerning CPM response, approximately 70% of chronic pain patients display a large and statistically significant reduction in their pain inhibition system relative to healthy controls, as evidenced in a meta-analysis by Lewis et al (2012). At the same time, various studies have found greater TSSP in chronic pain patients relative to healthy controls (Staud et al., 2001; Arendt-Nielsen et al., 2010; Petersen et al., 2015)

Altogether, the existing evidence supports that both CPM and TSSP could act as biomarkers of endogenous pain modulation to distinguish chronic pain patients. In fact, the efficiency of these endogenous modulatory pain systems could serve as a predictor of treatment outcomes with tES.

Lastly, the study of brain electrical activity recordings (EEG) in resting state and in response to noxious stimuli may also help to characterize the brain processing of nociceptive stimuli and how these signals are amplified or mitigated (González-Villar et al., 2019). For this reason, another purpose of this research is to evaluate the changes in neural patterns which occurred in chronic pain patients after transcranial electrical stimulation treatment. Specifically, we purport to make a time-frequency and connectivity analysis of the EEG paying special attention to those key frequency bands involved in nociceptive perception (Hu et al., 2013; Liberati et al., 2017; Fallon et al., 2018), namely Theta ($\approx 4-7$ Hz), Alpha ($\approx 8-12$ Hz) and Gamma ($\approx 35-70$ Hz). Brain activity will be recorded both in resting-state (Fallon et al., 2016; Choe et al., 2018) and in response to painful heat and cold stimulation (De Keyser et al., 2018; De Tomasso et al., 2014, 2017).

2. Objectives and hypothesis

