The main objective of this clinical trial is to test the efficacy of two different transcranial electrical stimulation techniques (tES) to modify dysfunction of central modulatory mechanisms of pain, and to improve symptoms and quality of life in refractory chronic pain patients.

In this vein, we hypothesize that transcranial electrical stimulation procedures will be more effective than sham to improve pain and related symptoms. Besides, central biomarkers of pain processing and modulation (i.e., CPM, TSSP and EEG) will be useful to predict the patient response to treatment and thus, the efficacy of these tES procedures.

Based in these principal ideas, we propose the following secondary or specific objectives:

- A. To analyse the relationship between the studied biomarkers and clinical pain characteristics of patients (intensity, location, frequency, duration, daily interference caused by pain).
- B. To stratify patients and propose profiles based on the selected biomarkers, which may be useful to improve diagnosis and to guide individualized treatment plans.
- C. To develop home-based treatment schemes for patients with refractory chronic pain. We will assess if tES procedures are safe, feasible and acceptable for the at-home management of this medical condition.
- D. To test if tES techniques are self-manageable by patients and to observe the impact of this treatment in the caregiver-burden declared by the reference person.
- E. To test the efficacy of tDCS (Direct current) versus tACS (Alternant current) to modify dysfunction of central endogenous analgesia (i.e., CPM and TSSP) and to reduce pain and related symptoms in the patients, in a placebo-controlled clinical trial.
- F. To analyze how the different tES techniques (tDCS and tACS) affect brain oscillatory activity, and to test if the changes in oscillatory activity are related to pain relief.
- G. To test the power of the biomarkers/patients' stratification to predict treatment efficacy and to identify the characteristic of best responders patients.

- H. To assess the effect of sex/gender and other modulator variables (age, disease duration, medication, lifestyle, mood...) on all the analyses (central biomarkers, patients' stratification, response to treatment...).

3. Study design

The research is classified as a double-blinded, randomized clinical trial with one control group which receive a sham stimulation.

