activity, the spectral power of the oscillations and inter-site phase connectivity (Ploner et al., 2017). Secondly, we will analyse wave components of the contact heat evoked potentials (CHEPs) to obtain a neural correlate of the painful stimuli processing. For last, in order to study the modulatory role of attention in pain perception, we propose to obtain the evoked potential derived from a TSSP protocol, both paying exclusive attention to pain and during a simple cognitive task.

Besides, we will repeat the same procedure of quantitative sensory testing to ascertain its reliability. Finally, the following questionnaires will be used to get an accurate measure of some key symptoms and problems which usually accompanies chronic pain:

- Hospital Anxiety and Depression Scale (HADS; Cabrera et al., 2015). It represents a really useful tool to assess mood state and screen for depressive or anxiety disorders, which frequently cooccurs with chronic pain.
- Modified Fatigue Impact Scale (MFIS; Duarte et al., 2017; Kos et al., 2005), which accounts for the physical, emotional and social components of fatigue. Fatigue usually accompanies chronic pain conditions and results in great limitations for the daily functioning of patients.
- Pittsburgh Sleep Quality Index (PSQI; Macías & Royuela, 1996). This inventory inquiries into several areas about the sleep patterns, such as the related disorders, the self-perceived quality or the time passed until falling asleep.
- Zarit Burden Interview (Martín et al., 1996). This instrument is used with the principal caregivers of the patients to assess the stress and negative feelings associated with the caring tasks. Thus, it represents the core of the evaluation protocol for caregiver, and it intends to pay attention to this figure but also to add information about the patient autonomy.

In sum, all the proposed questionnaires assess relevant clinical variables which are expected to be improved by tES treatment. Therefore, changes observed in them between pre- and post-evaluation will be subjected to statistical analysis and taken as efficacy indices of treatment.

However, there are some other variables which, despite not expecting to be modified, could influence the treatment outcomes for better or worse. We refer to social support, self-perceived stress, catastrophizing thinking and beliefs about controllability of pain

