The main quantitative statistical analyses to assess the efficacy of transcranial electrical stimulation techniques consist of ANOVA-tests of repeated measures with three groups. Time-measures for each of the above-mentioned endpoints are taken as intragroup variables (pre vs. post), whereas intergroup measures refer to the received stimulation or treatment (tDCS vs. tACS vs. Sham). Thus, both clinical variables (for example, pain intensity, fatigue, sleep quality, disease severity and interference) and potential biomarkers (including brain oscillatory activity registered by EEG, CPM and TSSP response) are considered as intragroup variables.

Those covariates which show a significant correlation with clinical outcomes will be also included in their correspondent ANOVA analysis. These potential covariates are basically age, self-perceived stress, social support, catastrophism and medication intake.

All these statistical analyses will be repeated in separated groups of patients, created in the basis of sex, type and duration of chronic pain, among other characteristics. The objective is to assess whether the clinical outcomes depend on sex or diagnosis, as each tES could be more effective for specific diseases.

CPM/TSSP response and EEG pattern observed before the tES application are also regarded as potential predictors of the treatment efficacy. Thus, the pre-treatment indexes of these biomarkers will be used as independent variables in *Linear regression models*, which includes the clinical improvement in each endpoint as dependent measure. The procedure will be repeated with *Logistic regression analysis* establishing the respondent vs. no-respondent categories as dichotomic variable.

For last, we will register and assess the percentage of dropouts with their respective motives, in order to obtain an index of the feasibility of home-based tES approach. Client

satisfaction index and caregiver interview will also include questions about the capability of participants to manage with tES devices, data which will be qualitatively analysed.

8. Chronogram

WORKING PLAN (WP)		3	6	9	12	15	18	21	24	27	30	33	36
TASK	\ MONTH												
WP1. Development and selection of assessment and monitoring tools for refractory chronic pain patients													
Task 1.1.	Review of the literature and identification of the most common and important variables used as outcomes in clinical trials with chronic pain population.												

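### Biomarker prediction of response is tested only by regressions fitted and read in the same 120 patients, for every endpoint, with an open-ended predictor set and no internal validation or multiplicity rule

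*Combined protocol and SAP*

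**What the plan says.** Section 2 states as a hypothesis that the central biomarkers "will be useful to predict the patient response to treatment and thus, the efficacy of these tES procedures". Objective G is to test their power "to predict treatment efficacy and to identify the characteristic of best responders patients".

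The matching analysis is one paragraph of section 7. It begins: "CPM/TSSP response and EEG pattern observed before the tES application are also regarded as potential predictors of the treatment efficacy". The first step is ordinary linear fitting, where "the pre-treatment indexes of these biomarkers will be used as independent variables in" the fit. The outcome of every such fit is the patient's change on one endpoint, and all endpoints are covered in turn. A logistic version then follows, "establishing the respondent vs. no-respondent categories as dichotomic variable".

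The paragraph names three families of predictor and gives no count. Other sections show how open the set is:

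- **EEG.** Section 1 plans time-frequency and connectivity analyses in three bands (theta, alpha, gamma). Section 6.2 adds a resting recording, contact heat evoked potentials and a further condition: "we propose to obtain the evoked potential derived from a TSSP protocol, both paying exclusive attention to pain and during a simple cognitive task".
- **CPM and TSSP.** Section 6.2 says that these protocols are not yet fully defined. It allows two kinds of test stimulus and one or two conditioning stimuli for CPM.

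No section gives a hold-out set, cross-validation, bootstrap, shrinkage, multiplicity adjustment, performance measure, criterion for calling a biomarker predictive, or significance level for these models.

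**The concern.** A regression fitted and judged in the same patients overstates how well it will predict in new ones. The overstatement grows with the number of predictors relative to the number of patients, or of responders in the logistic model. Here the number of predictors is open, the models are repeated for every endpoint in both linear and logistic form, and no rule says what result would count as prediction. A biomarker profile of good responders could therefore be reported from noise.

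At stake are the second hypothesis and objective G. The plan calls the caregiver question exploratory (section 4), but it does not give the prediction question that label. The comparison of tDCS, tACS and sham on pain intensity does not depend on these models.

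**Working it through.** **The plan's own figure.** The only computed figure is the total of 21 patients in section 4. Inputs: f = 0.68, alpha 0.01, power 0.99, 3 groups, 2 measurements. For the within-between interaction, with an assumed correlation of 0.5 between measurements:

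lambda = f² × N × m / (1 − rho) = 0.4624 × 21 × 2 / 0.5 = 38.84, on 2 and 18 df, giving power 0.994.

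The 21 is reproduced. It concerns the repeated-measures ANOVA and says nothing about the prediction models, for which the plan gives no figure.

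**Inputs for the prediction models**

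- n = 120 (section 4).
- Responder: at least 30% improvement (sections 6.2 and 7). The rate is not given; 35% is assumed, so 120 × 0.35 = 42 responders.
- Predictors: not given. Lower case 3, one per family. Assumed upper case 15: three EEG bands in four recordings (3 × 4 = 12), plus two CPM indexes and one TSSP index. That leaves 42/3 = 14 or 42/15 = 2.8 responders per predictor.
- Endpoints: Table 1 has 1 primary and 13 secondary rows, 14 in all.
- Significance level: none stated for these models, so 0.05 and 0.01 are both shown. The 0.01 appears in section 4 for the sample size.

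**One endpoint, one model, biomarkers unrelated to outcome**

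Expected apparent R2 = p/(n − 1): 3/119 = 2.5%; 15/119 = 12.6%.

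Chance of at least one false predictor, treating the tests as independent, = 1 − (1 − alpha)^p:

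- alpha 0.05: 1 − 0.95³ = 14%; 1 − 0.95¹⁵ = 54%.
- alpha 0.01: 1 − 0.99³ = 3%; 1 − 0.99¹⁵ = 14%.

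Simulation (600 to 3,000 null data sets per cell, independent standard normal predictors, n = 120) agrees:

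| Predictors | Apparent R2 | Apparent AUC | Any p<0.05 | Any p<0.01 |
|---|---|---|---|---|
| 3 | 2.5% | 0.59 | 14–16% | about 3% |
| 6 | 5.1% | 0.63 | 25% | 5.5% |
| 10 | 8.4% | 0.67 | 37% | 10% |
| 15 | 12.6–12.8% | 0.71 | 52–55% | about 13% |

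Where the fitted models were scored in new patients (3, 6 and 10 predictors), mean AUC was 0.50. With 15 predictors, correlating them at 0.5 leaves the AUC at 0.71 and gives any p<0.05 in about half of trials. Changing the responder rate to 20% or 50% gives an AUC of 0.75 or 0.70.

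The overall F-test rejected in 4% to 6% of null trials and mean adjusted R2 was about 0, with 3 or with 15 predictors.

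**All 14 endpoint rows, linear models only**

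With 3 predictors there are 3 × 14 = 42 tests. If independent, 1 − 0.95⁴² = 88%. Simulated (2,000 runs) with correlation between endpoints of 0, 0.3 and 0.6, the chance of at least one false p<0.05 is 88%, 80% and 64%, with about 2 false results on average. At p<0.01 the chances are 37%, 30% and 22%. With 6 predictors the p<0.05 range is 87% to 99%. The logistic repeats add to this.

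The 14 is a row count. Several rows hold more than one instrument, and the satisfaction row is collected only after treatment.

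**The case against.** The strongest reply is that the size of the problem rests on a number that the plan does not contain. Section 7 names three families and does not say that all indexes enter one model. Section 6.2 ties spectral power and connectivity to the resting recording, and evoked potentials to the others, so crossing three bands with four recordings is a construction. With a single three-predictor model the optimism is modest. This stands, and it is why the result is given as a range with 15 as an assumed upper case. Separate models per family would ease the responders-per-predictor problem but not the multiplicity.

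A reader might infer that useless biomarkers are bound to look predictive. The documents do not support that. For one endpoint the chance of a false predictor runs from about 2–3% (3 predictors, p<0.01) to about 55% (15 predictors, p<0.05). A false finding becomes likely only over the whole set of endpoints.

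A reader might also infer that nothing in the results could expose the problem. That too goes beyond the documents. Ordinary linear regression output includes an overall F-test and adjusted R2, and both behave correctly under the null. What remains is that the plan does not commit to reporting either, and they judge one linear model at a time.

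Finally, AUC is not a measure that the plan names, these objectives are listed as secondary or specific, and section 7 speaks only of potential predictors. All true. The hypothesis in section 2 is nevertheless worded as a claim of usefulness, and the plan gives no other way to test it.

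**Conclusion.** The concern holds as a gap between the aim and the method. The plan sets out to show that biomarkers predict response, and its only test is in-sample regression over an unspecified predictor set and every endpoint, without internal validation or a multiplicity rule.

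In one null model at n = 120, the apparent AUC exceeds the true 0.50 by about 0.09 (3 predictors) to 0.21 (15 predictors), and apparent R2 is 2.5% to 13%. Over the 14 rows of Table 1, at least one false p<0.05 is more likely than not even with 3 predictors (64–88%); at p<0.01 the chance is 22–37%.

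These figures assume biomarkers with no relation to outcome, complete data on 120 patients, 35% responders for the AUC, and correlation between endpoints of 0 to 0.6. Dropout, or fitting in fewer patients, would increase the optimism. The primary efficacy comparison is not affected. The change should be made, but the trial's main conclusion does not depend on it.

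**What to change.** In section 7:

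1. Name before analysis a short list of CPM, TSSP and EEG indexes for the primary endpoint, for example one per family.
2. Report R2 and AUC corrected for optimism by bootstrap or repeated cross-validation, with any variable selection repeated inside each resample, and give the overall model test alongside.
3. Base any statement that the biomarkers are useful for prediction on the corrected values.
4. Label all other biomarker-endpoint models exploratory.

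A comparison with a model of clinical variables alone would be informative but is optional.

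The cost is analysis time: no extra patients, visits or measurements. The downside is that the reported predictive figures will be less favourable.

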Pain thresholds are defined as the minimum intensity which must reach a stimulus to become in painful, as perceived and reported by the own person. Pressure pain threshold will be calculated using a digital handheld algometer (Wager Force One Model) which puts progressively heavier pressure over the skin surface. Heat pain threshold is obtained with a computerized thermal stimulator which progressively enhances the temperature of the skin with a small contact metal plate. In both cases, pressure and temperature increases to a constant pre-fixed rate, until the participant press a button to indicate she/he starts to feel pain. Pressure pain threshold is measured in kPa, whereas heat pain threshold is established as the temperature in degrees Celsius.

Although the specific CPM and TSSP protocols are not completely defined yet, we count with a wide catalogue of usually used instruments and equipment to perform these tests (Fernandes et al., 2019; O'Brien et al., 2018)

Conditioned Pain Modulation requires of two different painful stimuli applied in heterotopic body areas; thus, the conditioning stimuli (CS), tonic in nature, reduces the pain sensations from the phasic test stimuli (TS). As CS, we will use the ischemic pain produced by pressure cuff and/or the cold pressor test, which means the participant have to immerse their non-dominant hand into cold water. Regarding TS, we opt for the same procedures as to calculate the pain thresholds (i.e., digital handheld algometer and thermal stimulator), given that we aim to compare these isolated thresholds with those obtained

while the CS is present. The difference between these two measures is established as the CPM index.

Tentatively, Temporal Summation of Second Pain (TSSP) will be evoked with the thermal stimulator. After establishing the parameters which corresponds to a medium pain level (5/10 NRS) for each participant, it will be applied ten repetitive pulses with that temperature over the skin, separated by two and a half seconds. Patients have to rate the pain intensity which produces the first, fifth and last stimuli. The difference in pain intensity between the first and last pulse is established as the TSSP index.

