(Adams & Turk, 2015; Keefe et al., 2004; Jensen et al., 2011). Thus, these factors must be taken into account when assessing the efficacy of tES intervention and we intend to account them as covariates in statistical analysis.

Changes observed in criteria variables between pre- and post-evaluation must be equal or higher than the 30%, in order to ensure their clinical significance. It means that the improvement observed in self-reported questionnaires and in sensory testing (except for EEG) have to achieve or surpass the 30% of the original outcome. The direction of these differences depends on the specific scale; for example, it is expected a reduction in the global MPI score after treatment, but also a rise in pain thresholds. In the case of EEG, the analysis pre-post treatment are only subjected to the statistical significance. However, changes in brain activity patterns attributed to the tES will be tried to relate with improvement in clinical features.

Although all explained measurements are considered as success criteria of treatment, we selected pain intensity as the primary end point, taken as the average obtained from daily numerical rating scale. In this sense, participants will be classified into responders when they report, at least, a 30% decrease in their pain intensity. The rest of the variables are taken as secondary end points and are also regarded as treatment-efficacy indexes, basically the pain thresholds, life quality, physical functioning, interference caused by pain, pain unpleasantness, sleep quality, depression/anxiety, fatigue, caregiver burden and CPM/TSSP responses.

Table 1: End points of the clinical trial and their respective evaluation instruments

End points		Assessment tools
Primary end point	Pain intensity	Numerical Rating Scale of eleven points (0-10 NRS). Average obtained from daily self-reports during the fifteen days before treatment and the fifteen days after treatment.
Secondary end points	Global severity of chronic pain syndrome	Global and subscales scores of Multidimensional Pain Inventory (MPI).
	Interference caused by pain in daily living	Subscale score of Multidimensional Pain Inventory (MPI). Numerical Rating Scale of eleven points (0-10 NRS). Average obtained from daily self-reports during the fifteen days before treatment and the fifteen days after treatment.

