Besides, we will conduct simple ANOVA analyses to compare these indexes of pain processing and modulation (CPM, TSSP, EEG) between specific groups of patients, divided by type/origin of chronic pain and sex. We reserve the possibility of making *Cluster analyses* in the basis of the mentioned central biomarkers, following by an ANOVA comparison of clinical features between the emerged groups.

Besides, participants will be classified into CPM and TSSP respondents or non-respondents taking into account their results in these sensory tests. Those patients who report a significant increment in pain thresholds will be considered respondents; whereas the opposite applies for TSSP, as it must be detected a significant increase in perceived pain intensity in the last pulse compared to the first one. Depending on the proportions observed, it could be useful to divide TSSP respondents based on the degree of the pain sensitization. Regarding this sample division, we can compare the clinical profile of respondents and non-respondents patients using *Chi square statistic*.

As far as intervention efficacy is concerned, qualitative analyses will focus on differentiating the patients who effectively respond to treatment (Treatment-respondents) from those who do not improve (Non-treatment-respondent). Respondents are those

participants whose improvement in a certain clinical variable are equal or higher than the 30%; whereas non-respondents are all those who do not comply with this criterion. This variation is extracted from the comparison of pre- and post-treatment measurements.

Therefore, for each of the endpoints, we will obtain a number/percentage of respondents and non-respondents. Using the *Chi-square test*, we will compare the proportion of respondents between treatment groups to identify the most efficacious stimulation procedure. A separated analysis will be done for each described endpoint, which define what a respondent is.

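### Baseline CPM and TSSP share a reading with change in CPM, in TSSP and (CPM only) in same-modality pain threshold, so those regressions can show a predictor with no stimulation effect

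*Combined protocol and SAP*

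**What the plan says.** Section 7 (Data analysis plan) states that pre-treatment CPM/TSSP and EEG "are also regarded as potential predictors of the treatment efficacy". It continues that "the pre-treatment indexes of these biomarkers will be used as independent variables in" models fitted by linear regression. The outcome of those models is improvement, taken endpoint by endpoint ("which includes the clinical improvement in each endpoint as dependent measure"), and the exercise is repeated by logistic regression on responder status. On how improvement is obtained, the same section says: "This variation is extracted from the comparison of pre- and post-treatment measurements".

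Section 6.2 and Table 1 list the secondary endpoints. They include pain thresholds and "depression/anxiety, fatigue, caregiver burden and CPM/TSSP responses". The 30% rule covers sensory tests too: "improvement observed in self-reported questionnaires and in sensory testing (except for EEG) have to achieve or surpass the 30% of the original outcome".

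Section 6.2 builds CPM from the threshold measured alone and the threshold measured during the conditioning stimulus: "The difference between these two measures is established as the CPM index". The TSSP index is the last pulse rating against the first and contains no threshold.

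On the second pre-treatment visit, section 6.2 says "we will repeat the same procedure of quantitative sensory testing to ascertain its reliability", while section 6.1 makes that repeat optional. Neither section assigns one session to the predictor and the other to the baseline. Section 7 states no arm term and no biomarker-by-arm interaction for these regressions.

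**The concern.** When the outcome is post minus pre and the predictor is the same pre reading, the measurement error in that reading enters both sides with opposite signs. A patient who scores low by chance looks like a poor modulator and then appears to improve. That is regression to the mean, and it occurs with or without current.

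The threshold endpoint has a weaker form of the same problem. A chance-low isolated threshold raises baseline CPM and also raises the apparent threshold gain.

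The main hypothesis and objective G ask whether these biomarkers predict response and identify the best responders, and objective B wants profiles to guide individual treatment. For the coupled pairings the plan could report that patients with the poorest CPM gain most CPM, or that good CPM predicts threshold gain, when stimulation did nothing.

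**Working it through.** The plan gives no figure for these regressions, so there is none to reproduce.

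**Inputs from the documents.** Total 120, allocated 40/40/20 (sections 3 and 4): 0.8 × 120 = 96 active, 48 per active arm, and 0.2 × 120 = 24 sham. No alpha is stated for the regressions; 0.01 appears only in the sample size calculation.

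**Assumed.** Test-retest reliability (ICC), which the documents do not give; no stimulation effect; equal variance before and after.

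**1. An index against its own change.** With unit variances and correlation ICC, cov(pre, post − pre) = ICC − 1 and var(post − pre) = 2(1 − ICC), so

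r = −√((1 − ICC)/2).

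By Fisher's z, the chance of p<0.05 is about Φ(atanh|r|·√(n − 3) − 1.96). At ICC 0.8 and n = 96: r = −√0.1 = −0.316; 0.327 × √93 = 3.16; 3.16 − 1.96 = 1.20; Φ = 0.885.

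| ICC | r | n=96, α 0.05 | n=96, α 0.01 | n=120, α 0.05 | n=48, α 0.05 | n=24, α 0.05 |
|---|---|---|---|---|---|---|
| 0.4 | −0.55 | 100% | 100% | 100% | 98.5% | 80.5% |
| 0.6 | −0.45 | 99.6% | 98.1% | 99.9% | 89.8% | 59.7% |
| 0.8 | −0.32 | 88.5% | 72.0% | 94.3% | 59.4% | 32.3% |
| 0.9 | −0.22 | 59.2% | 35.1% | 69.2% | 33.2% | 18.1% |

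Simulation at n = 96 gives about 100%, 99.7%, 89% and 59%. The last two columns show that separate regressions per arm do not help: arm size alone can make a slope significant in an active arm and not in sham.

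**2. Averaging two sessions before and two after.** At ICC 0.8 the reliability of the mean is 2 × 0.8/1.8 = 0.889, so r = −√(0.111/2) = −0.24 and p<0.05 in about 64% of trials at n = 96.

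**3. Baseline CPM against threshold change, same modality.** Scale the threshold variance to 1. Let v = 1 − reliability be the error variance of a threshold reading, s the share of error common to both thresholds in a session, and V the variance of the true CPM effect (assumed 0.25). Then

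r = (1 − s)v / √((V + 2(1 − s)v) × 2v).

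- s = 0: reliability 0.7 gives 0.3/√(0.85 × 0.6) = 0.42; reliability 0.9 gives 0.1/√(0.45 × 0.2) = 0.33. At n = 96, p<0.05 in 99% and 92%.
- s = 0.5: 0.15/√(0.55 × 0.6) = 0.26 and 0.05/√(0.35 × 0.2) = 0.19. Simulations give 46-74%.
- s = 1: r = 0, about 5%.

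Adjusting the threshold model for baseline threshold does not cure it: with s of 0 or 0.5 and N = 120, baseline CPM is still significant in 47-97% of null trials (threshold reliability 0.5-0.9).

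**4. Uncoupled pairs as a control.** TSSP on threshold change and CPM on diary pain change stay at 4-6%.

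**5. Candidate remedies, same null.**
- *Biomarker-by-arm interaction (96 v 24).* Linear: 3.5-6.1% for CPM change and 4.3-6.3% for threshold change (s of 0 or 0.5). Logistic: 2-4% in one set of runs and 6-9% in another. In a check, Wald tests fell at the lower end and likelihood-ratio tests higher.
- *Session-1 predictor, session-2 baseline, linear.* 4-6% if the trait is stable. If readings correlate 0.8 across one interval and 0.7 across two, r = (0.7 − 0.8)/√(2 − 1.6) = −0.16, and about 34% of trials are significant at n = 96.
- *The same split, logistic on 30% response.* 15-53% false positives remain at ICC 0.6-0.8 (mean index assumed 1-2 SD); a run for TSSP gave 23-73%. The 30% threshold scales with baseline, so a patient with a small true index passes it more easily by noise, and the session-1 reading still tracks that true index.

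**The case against.** The strongest reply is about reach. Section 7 asks for clinical improvement, and two paragraphs earlier it separates clinical variables from potential biomarkers such as CPM and TSSP. The own-change pairings may therefore not be intended. Against that, the regression sentence covers every endpoint, Table 1 makes CPM, TSSP and thresholds endpoints, and the 30% rule is applied to sensory testing. The wording includes them unless it is changed.

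A second reply is that the figures are a high case: single readings, no dropout, no stated reliability, and CPM/TSSP protocols that section 6.2 calls incomplete. This stands in part. Averaging sessions lowers 89% to 64% at ICC 0.8, and at ICC 0.9 the single-reading figure is 59%. None of these is near 5%.

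A third reply is that the real gap is the missing comparison with sham. That is largely right, and it decides the remedy: regression to the mean is the same in sham, so the interaction removes it.

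Three stronger readings are tempting and not supported:
- *Baseline CPM or TSSP is the value subtracted in threshold change.* It is not. CPM only contains the isolated threshold, in the same modality, and TSSP shares no term with thresholds.
- *A false predictor is certain.* That depends on a reliability the documents do not give and, for thresholds, on how much error is shared within a session.
- *Objective G as a whole is compromised.* Diary pain and the questionnaires do not share a reading with CPM or TSSP.

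**Conclusion.** The defect holds for three pairings: CPM on CPM change, TSSP on TSSP change, and CPM on same-modality threshold change. At the planned size, own-change slopes would be significant without any stimulation effect in most trials up to an ICC of about 0.9. The threshold slope ranges from nominal to near certain according to shared within-session error.

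These sizes rest on assumed reliabilities, equal variances and, for thresholds, V = 0.25. I give no single figure for the same-reading logistic models. Regression to the mean and the scaling 30% threshold reinforce each other for CPM, but they oppose each other for TSSP if improvement there means a fall.

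The primary endpoint and the group-by-time comparisons of efficacy are untouched. This should be corrected before analysis, but it does not threaten the trial's main result.

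**What to change.** In section 7, for the CPM, TSSP and pain threshold endpoints:

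1. Judge prediction of treatment efficacy by the biomarker-by-arm interaction (active v sham), in both the linear and the logistic models, and not by a pooled or within-arm slope.
2. If a slope is also reported in the linear models, take the predictor from pre-treatment session 1 and the baseline from session 2. State that this assumes a stable trait.
3. Do not use that split for the 30% responder models. There, and wherever the session-2 repeat was not done, report only the interaction or drop the three coupled pairings.

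Diary pain and the questionnaires do not need the session split.

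The cost is a few sentences and no new data. The price is precision: with equal predictor variance in both groups, the standard error of the interaction is √(1/96 + 1/24)/√(1/120) = √6.25 = 2.5 times that of the pooled slope at 120. A null interaction would therefore be weak evidence. A single-session predictor is also slightly noisier than a two-session mean.
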